17.2. Definitions and Classification

Adverse event definitions are provided in Table 17.2-1. Administrative edits were made on the safety definitions from ISO 14155 and MEDDEV 2.7/3 for clarification purposes.

Table 17.2-1: Safety Definitions

Term	Definition
Adverse Event (AE) Ref: ISO 14155 Ref: MDCG 2020-10/1	Any untoward medical occurrence, unintended disease or injury, or any untoward clinical signs (including an abnormal laboratory finding) in subjects, users or other persons, in the context of a clinical investigation and whether or not related to the study medical device and whether anticipated or unanticipated. NOTE 1: This includes events related to the study medical device or comparator. NOTE 2: This definition includes events related to the procedures involved. NOTE 3: For users or other persons, this definition is restricted to events related to the study medical device.
Adverse Device Effect (ADE) Ref: ISO 14155 Ref: MDCG 2020-10/1	Adverse event related to the use of the study medical device NOTE 1: This includes any adverse event resulting from insufficiencies or inadequacies in the instructions for use, the deployment, the implantation, the installation, the operation, or any malfunction of the study medical device. NOTE 2: This definition includes any event resulting from use error or intentional misuse of the study medical device. NOTE 3: This includes 'comparator' if the comparator is a medical device.
Serious Adverse Event (SAE) Ref: ISO 14155 Ref: MDCG 2020-10/1	Adverse event that led to any of the following: a) death, b) serious deterioration in the health of the subject, users or other persons as defined by either: 1) a life-threatening illness or injury, or 2) a permanent impairment of a body structure or a body function, including chronic diseases, or 3) in-patient hospitalization or prolongation of existing hospitalization, or 4) medical or surgical intervention to prevent life-threatening illness or injury or permanent impairment to a body structure or a body function c) foetal distress, foetal death, or a congenital abnormality or birth defect including physical or mental impairment.

Table 17.2-1: Safety Definitions

Term	Definition
	
NOTE 1: Planned hospitalization for a pre-existing condition, or a procedure required by the clinical investigational plan, without a serious deterioration in health, is not considered a serious adverse event.


Serious Adverse Device Effect (SADE)
 
Ref: ISO 14155
 
Ref: MDCG 2020-10/1
	
Adverse device effect that has resulted in any of the consequences characteristic of a serious adverse event.

Unanticipated Adverse Device Effect (UADE)
 
Ref: 21 CFR Part 812
	
Any serious adverse effect on health or safety or any life-threatening problem or death caused by, or associated with, a device, if that effect, problem, or death was not previously identified in nature, severity, or degree of incidence in the investigational plan or application (including a supplementary plan or application), or any other unanticipated serious problem associated with a device that relates to the rights, safety, or welfare of subjects.

Unanticipated Serious Adverse Device Effect (USADE)
 
Ref: ISO 14155
 
Ref: MDCG 2020-10/1
	
Serious adverse device effect which by its nature, incidence, severity, or outcome has not been identified in the current risk assessment.
 
NOTE 1: Anticipated serious adverse device effect (ASADE) is an effect which by its nature, incidence, severity or outcome has been identified in the risk assessment.

Serious Health Threat
 
Ref: ISO 14155
	
Signal from any adverse event or device deficiency that indicates an imminent risk of death or a serious deterioration in the health in subjects, users or other persons, and that requires prompt remedial action for other subjects, users or other persons.
 
NOTE 1: This would include events that are of significant and unexpected nature such that they become alarming as a potential serious health hazard or possibility of multiple deaths occurring at short intervals.

Device Deficiency
 
Ref: ISO 14155
 
Ref: MDCG 2020-10/1
	
An inadequacy of the study medical device related to its identity, quality, durability, reliability, usability, safety or performance.
 
NOTE 1: Device deficiencies include malfunctions, use errors, and inadequacy in the information supplied by the manufacturer including labelling.
 
NOTE 2: This definition includes device deficiencies related to the device under study, or the comparator.

The following definitions will be used for defining hospitalization or prolongation of hospitalization for SAE classification purposes:
	

Hospitalizations
	
Hospitalization does not include:
 
 • emergency room visit that does not result in in-patient admission 
Note: although an emergency room visit does not itself meet the definition for hospitalization, it may meet other serious criteria (e.g. medical or surgical intervention to prevent permanent impairment or damage)
 
 • elective and pre-planned treatment/surgery for a pre-existing condition that is documented in the subject's record at the time of consent/enrollment

Table 17.2-1: Safety Definitions

Term	Definition
	
 admission for social reasons and/or respite care in the absence of any deterioration in the subject's general condition (e.g. subject is homeless, caregiver relief) 
pre-planned, protocol-specified admission related to the clinical study (e.g. procedure required by protocol)

Prolongation of hospitalization	
In-patient admission to the hospital that is prolonged beyond the expected standard duration for the condition under treatment.
 
Note: new adverse events occurring during the hospitalization are evaluated to determine if they prolonged hospitalization or meet another SAE criteria.

Underlying diseases are not reported as AEs unless there is an increase in severity, location, or frequency, beyond the expected course or progression of the disease, during the investigation. Death should not be recorded as an AE, but should only be reflected as an outcome of a specific SAE.

Hospitalization is defined as any in-patient admission regardless of duration of stay. Emergency room admissions and outpatient visits are not considered hospitalizations.

Any adverse event or complaint occurring in subjects who withdraw participation in the study and opt to remain implanted with the device should be reported to the Complaints Call Center as detailed in the "Directions for Use (DFU)".

In accordance with FDA regulations 21 CFR 820.3, a complaint is any written, electronic or verbal communication that alleges deficiencies related to the identity, design, quality, durability, reliability, safety, effectiveness or performance of a product after it is released for distribution.

Pregnancy will not be considered an adverse event. If a subject becomes pregnant, she may withdraw from the study or remain in the study at her discretion with concurrence of her physician.

NOTES:

1. For the purposes of this study, hospitalization is defined as any in-patient admission.
2. Hospitalizations occurring for the purpose of performing a planned procedure as per routine care such as implant procedures, or follow-up visits, are not to be reported as a SAE. However, complications or adverse events that occur during the planned procedure should be reported as (S)AEs if they meet the protocol specified definitions.
3. Elective/planned hospitalization(s) need not be reported as an SAE. However, complications or adverse events that occur during an elective/planned hospitalization, should be reported as (S)AEs if they meet the protocol specified definitions.

4. In the event of subject death during the conduct of the study, efforts should be made to perform an autopsy.
5. Sensations or side effects that occur during the programming session should not be reported as AEs. However, sensations or side effects caused by the final programming parameters (including active contact, pulse width, frequency, and amplitude) that persist or occur after the completion of the programming will be reported as AEs.
6. Lack of efficacy/decreased therapeutic response will not be collected as AEs. Also, return of the patient's pain symptoms to their pre-SCS level does not meet the criteria for an AE.
7. Clinically significant worsening of symptoms, beyond the pre-SCS symptoms or the expected course or progression of the disease, should be reported as an AE.
8. Device/lead migration will not be collected as an AE. However, if the device/lead migration precipitated an AE, the AE should be reported in the *Adverse Event* eCRF. Device/lead migration should be documented in the *Device Deficiency* eCRF.
9. Device deficiencies, failures, malfunctions, and product nonconformities should not be reported as adverse events. However, if an adverse event resulted from a device failure or malfunction, that specific event would be recorded on the *Adverse Event* eCRF. Device deficiencies, failures, malfunctions, and product non-conformities should be documented in the *Device Deficiency* eCRF.

17.3. *Relationship to Study Device(s), (Device Under Study and Comparator Device, if applicable) and/or Study Procedure*

The Investigator must assess the relationship of the reportable AE to the study device(s), stimulation and/or procedure. See criteria in Table 17.3-1:

Table 17.3-1: Criteria for Assessing Relationship of Study Device(s) (Device Under Study and Comparator Device, if applicable) or Procedure to Adverse Event

Classification	Description
Not Related Ref: MDCG 2020-10/1	
Relationship to the device, comparator or procedures can be excluded when:
 
 - the event has no temporal relationship with the use of the study device or the procedures related to the use of the study device; - the serious event does not follow a known response pattern to the medical device (if the response pattern is previously known) and is biologically implausible; - the discontinuation of medical device application or the reduction of the level of activation/exposure - when clinically feasible – and reintroduction of its use (or increase of the level of activation/exposure), do not impact on the serious event; - the event involves a body-site or an organ that cannot be affected by the device or procedure; - the serious event can be attributed to another cause (e.g. an underlying or concurrent illness/ clinical condition, an effect of another device, drug, treatment or other risk factors); - the event does not depend on a false result given by the study device used for diagnosis, when applicable; - In order to establish the non-relatedness, not all the criteria listed above might be met at the same time, depending on the type of device/procedures and the serious event.
Unlikely Related Ref: MEDDEV 2.7/3	
The relationship with the use of the device seems not relevant and/or the event can be reasonably explained by another cause, but additional information may be obtained.
 
NOTE: Causality “Unlikely Related” was added in compliance with MED DEV 2.7/3 rev 3 and will continue to be collected from the sites.

Possibly Related Ref: MDCG 2020-10/1	
The relationship with the use of the study device or comparator, or the relationship with procedures is weak but cannot be ruled out completely. Alternative causes are also possible (e.g. an underlying or concurrent illness/ clinical condition or/and an effect of another device, drug or treatment). Cases where relatedness cannot be assessed or no information has been obtained should also be classified as possible.

Probably Related Ref: MDCG 2020-10/1	
The relationship with the use of the study device or comparator, or the relationship with procedures seems relevant and/or the event cannot be reasonably explained by another cause.

Table 17.3-1: Criteria for Assessing Relationship of Study Device(s) (Device Under Study and Comparator Device, if applicable) or Procedure to Adverse Event

Classification	Description
Causal Relationship Ref: MDCG 2020-10/1	
The serious event is associated with the study device, comparator or with procedures beyond reasonable doubt when:
 
 - the event is a known side effect of the product category the device belongs to or of similar devices and procedures; - the event has a temporal relationship with the study device use/application or procedures; - the event involves a body-site or organ that 
 -the study device or procedures are applied to; -the study device or procedures have an effect on; - the serious event follows a known response pattern to the medical device (if the response pattern is previously known); - the discontinuation of medical device application (or reduction of the level of activation/exposure) and reintroduction of its use (or increase of the level of activation/exposure), impact on the serious event (when clinically feasible); - other possible causes (e.g. an underlying or concurrent illness/ clinical condition or/and an effect of another device, drug or treatment) have been adequately ruled out; - harm to the subject is due to error in use; - the event depends on a false result given by the study device used for diagnosis, when applicable; 
- In order to establish the relatedness, not all the criteria listed above might be met at the same time, depending on the type of device/procedures and the serious event.

17.4. *Investigator Reporting Requirements*

The communication requirements for reporting to BSC are as shown in Table 17.4-1: Investigator Reporting Requirements.

Table 17.4-1: Investigator Reporting Requirements

Event Classification	Communication Method	Communication Timeline post-market studies* (MDCG 2020-10/1 MEDDEV 2.12/2 : GUIDELINES ON A MEDICAL DEVICE VIGILANCE SYSTEM)
Serious Adverse Event	Complete AE eCRF page with all available new and updated information.	
 • Within 10 business days after becoming aware of the event or as per local/regional regulations. • Reporting required through end of study.
	Provide all relevant source documentation (de-identified/ pseudonymized)	
 • When documentation is available • Upon request of sponsor

Event Classification	Communication Method	Communication Timeline post-market studies* (MDCG 2020-10/1 MEDDEV 2.12/2 : GUIDELINES ON A MEDICAL DEVICE VIGILANCE SYSTEM)
	for reported event upon request.	
Serious Adverse Device Effects	Complete AE eCRF page with all available new and updated information.	
 Within 2 business days of first becoming aware of the event or as per local/regional regulations. Reporting required through the end of the study
	Provide all relevant source documentation (de-identified/ pseudonymized) for reported event.	
 When documentation is available Upon request of sponsor
Device Deficiencies (including but not limited to malfunctions, use errors, and inadequacy in information supplied by the manufacturer, including labelling) Note: Any Device Deficiency that might have led to a serious adverse event if appropriate action had not been taken, intervention had not occurred, or if circumstances had been less fortunate is considered a reportable event.	Complete Device Deficiency CRF with all available new and updated information.	
 Within 2 business days of first becoming aware of the event. Reporting required through the end of the study
	Provide all relevant source documentation (de-identified/ pseudonymized) for reported event upon request.	
 Upon request of sponsor
Adverse Event including Adverse Device Effects	Complete AE eCRF page, which contains such information as date of AE, treatment of AE resolution, assessment of seriousness and relationship to the device.	
 Adverse Device Effects (or other key events of interest, e.g., Heart Failure): In a timely manner (e.g. recommend within 30 business days) after becoming aware of the information Adverse Events: In a timely manner (e.g. recommend within 30 business days) after becoming aware of the information Reporting required through end of study. Reporting required for all procedure and device (stimulation and hardware) related adverse events
	Provide all relevant source documentation (de-identified/ pseudonymized) for reported event.	
 Upon request of sponsor

Event Classification	Communication Method	Communication Timeline post-market studies* (MDCG 2020-10/1 MEDDEV 2.12/2 : GUIDELINES ON A MEDICAL DEVICE VIGILANCE SYSTEM)
----------------------	----------------------	---

The investigator must report Device and Procedure Related Adverse Events, Adverse Device Effects, Serious Adverse Events (regardless of relationship to device hardware, stimulation and/or procedure), and Device Deficiencies for each subject from the time of Information Consent through the end of study participation. AEs and Device Deficiencies may be reported via phone, fax or email if the electronic data capture (EDC) system is unavailable. The paper AE Notification Form or Device Deficiency Notification Form should be used to report AEs and/or device deficiencies during this time.

The Investigator must assess the potential relationship of all adverse events to the study device and/or to study procedures.

- Adverse events must be assessed according to their relationship to one of the following categories:
 - **Device Hardware-Related AEs:** AEs that can reasonably (i.e. Unlikely, Possibly, Probably and Causally Related) be attributed to the mere physical presence of the device or to deficiency of the device (i.e., an allergic response to device materials).
 - **Stimulation-Related AEs:** AEs that can reasonably (i.e. Unlikely, Possibly, Probably and Causally Related) be attributed to the effects of stimulation. A relationship to stimulation may be determined by demonstrating a predictable response to the alternating between stimulation-on and stimulation-off settings. However, a relationship to stimulation may also be reported without demonstrating a predictable response to the alternating between the stimulation-on and stimulation-off settings if in the opinion of the Investigator the AE is potentially related to stimulation.
 - **Procedure Related AEs:** AEs that can reasonably (i.e. Unlikely, Possibly, Probably and Causally Related) be attributed to a study protocol required procedure.

17.5. *Boston Scientific Device Deficiencies*

Device deficiencies for Boston Scientific devices will be documented and reported to BSC. If possible, the device(s) should be returned to BSC for analysis. Instructions for returning the device(s) will be provided from the study sponsor. Device deficiencies should also be documented in the subject's source records.

Device deficiencies are not adverse events. However, an adverse event that results from a device deficiency, would be recorded as an adverse event on the appropriate eCRF.

17.6. *Reporting to Regulatory Authorities / IRBs / Investigators*

BSC is responsible for reporting adverse event information to all participating Principal Investigators, IRBs and regulatory authorities, as applicable.

The Principal Investigator is responsible for informing the IRB, and regulatory authorities of UADEs and SAEs as required by local/regional regulations.

18. Informed Consent

Subject participation in this clinical study is voluntary. Informed Consent is required from each subject. The Investigator is responsible for ensuring that Informed Consent is obtained prior to the use of any study devices, study-required procedures and/or testing, or data collection.

The obtaining and documentation of Informed Consent must be in accordance with the principles of the Declaration of Helsinki, ISO 14155, any applicable national regulations, and local Ethics Committee and/or Regulatory authority, as applicable. The ICF must be accepted by BSC or its delegate (e.g. CRO), and approved by the site's IRB, or central IRB, if applicable.

Boston Scientific will provide a study-specific template of the ICF to investigators participating in this study. The ICF template may be modified to meet the requirements of the investigative site's IRB. Any modification requires acceptance from BSC prior to use of the form. The ICF must be in a language understandable to the subject. Privacy language shall be included in the body of the form or as a separate form as applicable.

The process of obtaining Informed Consent shall at a minimum include the following steps, as well as any other steps required by applicable laws, rules, regulations and guidelines:

- be conducted by the Principal Investigator or designee authorized to conduct the process,
- include a description of all aspects of the clinical study that are relevant to the subject's decision to participate throughout the clinical study,
- avoid any coercion of or undue influence of subjects to participate,
- not waive or appear to waive subject's legal rights,
- use native language that is non-technical and understandable to the subject or his/her legal representative,
- provide ample time for the subject to consider participation and ask questions if necessary,
- ensure important new information is provided to new and existing subjects throughout the clinical study.

The ICF shall always be signed and personally dated by the subject and by the investigator and/or an authorized designee responsible for conducting the informed consent process. The

original signed ICF will be retained by the site and a copy of the signed and dated document and any other written information must be given to the person signing the form.

Failure to obtain subject consent will be reported by BSC to the applicable regulatory authority according to their requirements (e.g., FDA requirement is within 5 working days of learning of such an event). Any violations of the informed consent process must be reported as deviations to the sponsor and local regulatory authorities (e.g. IRB), as appropriate.

If new information becomes available that can significantly affect a subject's future health and medical care, that information shall be provided to the affected subject(s) in written form via a revised ICF or, in some situations, enrolled subjects may be requested to sign and date an addendum to the ICF. In addition to new significant information during the course of a study, other situations may necessitate revision of the ICF, such as if there are amendments to the applicable laws, protocol, a change in Principal Investigator, administrative changes, or following annual review by the IRB. The new version of the ICF must be approved by the IRB. Acceptance by Boston Scientific is required if changes to the revised ICF are requested by the site's IRB. The IRB will determine the subject population to be re-consented.

19. Committees

19.1. *Safety Monitoring Process*

The BSC personnel from the BSC Medical Safety group review safety data as soon as it is reported, by the sites throughout the duration of the study. During scheduled monitoring activities, clinical research monitors further support this review through their review of source documents and other data information. The BSC Medical Safety group includes a physician with the necessary therapeutic and subject matter expertise to evaluate and classify the events into the categories outlined above.

20. Suspension or Termination

20.1. *Premature Termination of the Study*

Boston Scientific reserves the right to terminate the study at any stage but intends to exercise this right only for valid scientific or business reasons and reasons related to protection of subjects. Investigators, associated IRBs, and regulatory authorities, as applicable, will be notified in writing in the event of study termination.

20.1.1. *Criteria for Premature Termination of the Study*

Possible reasons for premature study termination include, but are not limited to, the following:

- Suspicion of an unacceptable risk, including serious health threat. In this case, the sponsor shall suspend the clinical investigation while the risk is assessed. The sponsor shall terminate the clinical investigation if an unacceptable risk which cannot be controlled is confirmed.

- Instructions by the IRB or regulatory authorities to suspend or terminate the clinical investigation.
- An enrollment rate far below expectation that prejudices the conclusion of the study.
- A decision on the part of Boston Scientific to suspend or discontinue development/marketing of the device.

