20.2. Definitions and Classification

Adverse event definitions are provided in Table 20.2-1. Administrative edits were made on the safety definitions from ISO 14155 and MEDDEV 2.7/3 for clarification purposes.

Table 20.2-1: Safety Definitions

Term	Definition
Adverse Event (AE) Ref: ISO 14155 Ref: MEDDEV 2.7/3	Any untoward medical occurrence, unintended disease or injury, or any untoward clinical signs (including an abnormal laboratory finding) in subjects, users or other persons, whether or not related to the study medical device. NOTE 1: This includes events related to the study medical device or comparator. NOTE 2: This definition includes events related to the procedures involved. NOTE 3: For users or other persons, this definition is restricted to events related to the study medical device.
Adverse Device Effect (ADE) Ref: ISO 14155 Ref: MEDDEV 2.7/3	Adverse event related to the use of the study medical device NOTE 1: This includes any adverse event resulting from insufficiencies or inadequacies in the instructions for use, the deployment, the implantation, the installation, the operation, or any malfunction of the study medical device. NOTE 2: This definition includes any event resulting from use error or intentional abnormal use of the study medical device.
Serious Adverse Event (SAE) Ref: ISO 14155 Ref: MEDDEV 2.7/3	Note: This definition meets the reporting objectives and requirements of ISO 14155 and MEDDEV 2.7/3. Adverse event that: a) Led to death, b) Led to serious deterioration in the health of the subject as defined by either: 1) a life-threatening illness or injury, or 2) a permanent impairment of a body structure or a body function, or 3) in-patient hospitalization or prolongation of existing hospitalization, or 4) medical or surgical intervention to prevent life-threatening illness or injury or permanent impairment to a body structure or a body function c) Led to fetal distress, fetal death, or a congenital abnormality or birth defect.

Table 20.2-1: Safety Definitions

Term	Definition
	NOTE 1: Planned hospitalization for a pre-existing condition, or a procedure required by the clinical investigational plan, without a serious deterioration in health, is not considered a serious adverse event.
Serious Adverse Device Effect (SADE) Ref: ISO 14155 Ref: MEDDEV 2.7/3	Adverse device effect that has resulted in any of the consequences characteristic of a serious adverse event.

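### Note 3 to the safety definitions exempts every planned admission from SAE reporting while the SAE definition exempts only some, so an event serious only through a scheduled admission can be left out of the SAE rate

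*Combined protocol and SAP*

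**What the plan says.** Each protocol defines a serious adverse event in a table (NAVITAS Table 20.2-1, ENVISION Table 17.2-1). Under criterion b)3 an adverse event that led to in-patient hospitalization is serious, and both texts count any in-patient admission, however short. NOTE 1 to the definition, worded alike in the two protocols, takes out "Planned hospitalization for a pre-existing condition, or a procedure required by the clinical investigational plan", provided there is no serious deterioration in health. ENVISION's table adds a Hospitalizations row. Its exclusion for elective care covers only "elective and pre-planned treatment/surgery for a pre-existing condition that is documented in the subject's record at the time of consent/enrollment". The row also excludes protocol-specified admissions, social or respite admissions, and emergency-room visits that do not end in admission.

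The numbered notes that follow each table return to the subject. Note 2 takes out "Hospitalizations occurring for the purpose of performing a planned procedure as per routine care such as implant procedures, or follow-up visits". Note 3 says, identically in both protocols, that "Elective/planned hospitalization(s) need not be reported as an SAE", and adds that "complications or adverse events that occur during an elective/planned hospitalization, should be reported as (S)AEs if they meet the protocol specified definitions".

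Neither protocol has pre-defined endpoints. Both commit to reporting the rate of device- and procedure-related AEs and of SAEs from consent to study exit (NAVITAS 7.1; ENVISION synopsis, Safety Parameters).

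**The concern.** Two rules in the same section cover the same admission. The table limits the exemption by the reason for admission; Note 3 does not. Its second sentence brings back events that happen during a planned stay, but says nothing about the event that made the stay necessary.

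The SAE rate is one of the few results these studies promise. If some sites follow the table and others Note 3, the pooled rate mixes two definitions across up to 30 sites per protocol. Seriousness also sets the reporting deadline, is a condition of the SADE and USADE categories, and triggers the investigator's duty to inform the IRB and authorities (NAVITAS 20.6, ENVISION 17.6).

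**Working it through.** The plan gives no figure on this point, so there is nothing to reproduce. The check is of the text, followed by the deadlines each reading leads to.

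**1. The exemptions side by side**

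| | SAE NOTE 1 (both protocols) | Hospitalizations row, elective care (ENVISION only) | Note 3 (both protocols) |
|---|---|---|---|
| Reason for admission | Pre-existing condition or plan-required procedure | Pre-existing condition | No limit |
| Timing | Planned | Pre-planned, with the condition on record at consent or enrollment | Elective or planned, no reference date |
| Severity proviso | No serious deterioration in health | None stated | None |
| What is restored | Not applicable | Not applicable | Only events arising during the stay |

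**2. A test case.** After consent a subject develops a device-related complication. It is not life-threatening and threatens no permanent impairment. It is treated during an in-patient stay booked in advance.

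- Under the table, criterion b)3 is met. The condition is not pre-existing, the stay is not required by the plan, and it is not social or respite care. The event is an SAE and, being device-related, a SADE.
- Under Note 3, the stay is planned and so need not be reported as an SAE. The complication came before the stay, so the second sentence does not restore it. No other seriousness criterion applies, and the event can be filed as non-serious.

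**3. Where the event then goes.** All SAEs are reportable, but non-serious events only if device- or procedure-related (NAVITAS 20.1 and 20.4; ENVISION 17.1 and 17.4). A related event changes count. An unrelated one can go unreported.

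**4. The deadline.** For a SADE in ENVISION Table 17.4-1, and for any SAE in the NAVITAS 20.4 table, it is "Within 2 business days of first becoming aware of the event or as per local/regional regulations". The other inputs come from the same two tables.

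| Event | NAVITAS: SAE | NAVITAS: non-serious | ENVISION: SAE | ENVISION: non-serious |
|---|---|---|---|---|
| Device-related | 2 business days | Timely, no number | 2 business days (SADE) | 30 business days, recommended |
| Procedure-related only | 2 business days | Timely, no number | 10 business days | 30 business days, recommended |
| Unrelated | 2 business days | Not reportable | 10 business days | Not reportable |

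In ENVISION the device-related event can arrive 30 − 2 = 28 business days later, and 30 / 5 = 6 weeks after the site learns of it. For a procedure-only event the difference is 30 − 10 = 20 business days.

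**5. What is not affected.** An event needing medical or surgical intervention to prevent life-threatening illness or injury, or permanent impairment, is serious under criterion b)4 without any admission. Device deficiencies have their own 2-business-day deadline in both protocols. Lead migration alone is not an AE under Note 8 and goes to the Device Deficiency form, so Note 3 is not what keeps it out of the SAE count.

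**6. Effect on the rate.** The shift equals the proportion of subjects who have no other SAE and whose event is serious only through a scheduled stay and is handled under Note 3. The documents give no explant, revision or in-patient rate from which to obtain it.

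**The case against.** The best defense is that Notes 2 and 3 speak of hospitalizations, not of the events behind them. On that reading a planned stay is simply not logged as an SAE in itself, and an adverse event that led to it is still judged by the table. A careful site could read it so. But where the admission is the only seriousness criterion, exempting it removes the ground for seriousness, and the second sentence omits the causal event. The text allows both readings.

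ENVISION has a further answer: its table says the hospitalization definitions there are the ones used for SAE classification. This weakens the conflict in ENVISION without removing it. The notes stand in the same section, Note 1 is also stated to apply for the purposes of the study, and no order of precedence is given. NAVITAS has neither the row nor the statement.

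The sponsor's Medical Safety group reviews and classifies reported events (NAVITAS 22.1, ENVISION 19.1). That limits drift between sites for related events, which still arrive as AEs. It cannot correct an unrelated event that was never submitted.

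Some stronger readings are tempting, and the documents do not support them:

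- A reader might infer that scheduled explants and revisions for device complications vanish from safety reporting. They do not: related events stay reportable, their rate is also a committed result, and criterion b)4 will keep some of them serious.
- Note 2 might be taken to exempt such procedures too. Its examples are "Hospitalizations occurring for the purpose of performing a planned procedure as per routine care such as implant procedures" and follow-up visits, so the unrestricted exemption rests on Note 3.
- The 2-business-day deadline might be read as covering every ENVISION SAE. It covers SADEs and device deficiencies; other SAEs have 10.

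**Conclusion.** The inconsistency is real and stands in the current text of both protocols. It concerns adverse events that arise after consent and are serious only because they led to a scheduled in-patient admission. For these, the table and Note 3 can give opposite classifications, with the changes of count and deadline shown above. It is clearer in NAVITAS than in ENVISION.

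The effect on the SAE rate has no supportable number. A reader might apply an assumed 2% to 10% to NAVITAS's 960 implants: 960 × 0.02 = 19.2 and 960 × 0.10 = 96 events. Dividing by 960 returns 2 to 10 percentage points, which is only the assumption restated. The 960 is itself a ceiling and one of three alternative enrollment stops (NAVITAS 10.4). The calculation also takes every case to be in-patient, none to meet criterion b)4, and every site to follow Note 3.

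These are post-market studies of commercial devices with no formal hypotheses, and a short clarification resolves the point. It should be fixed, but it does not put the studies in doubt.

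**What to change.** Make the following changes in both protocols:

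- Limit the first sentence of Note 3 to the admissions already exempted by SAE NOTE 1 and, in ENVISION, by the Hospitalizations row. Carry over NOTE 1's proviso about serious deterioration.
- Keep the second sentences of Notes 2 and 3, which preserve complications during a planned stay.
- Keep Note 2's exemption for the planned implant procedure itself. Neither table plainly exempts an implant done as routine care, so this part of Note 2 is needed.
- Add one sentence to both notes: an adverse event arising after consent that leads to an in-patient admission is assessed under the SAE definition even if the admission was scheduled.

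This changes reporting only, not the care of subjects. It costs a wording amendment and a site memo. The downside is somewhat more SAE reports and a slightly higher reported SAE rate.
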